Grade 4 confirmed bacterial infections	Discontinue acalabrutinib
Other	
Any non-COVID-19-related Grade 4 AE	Discontinue acalabrutinib
Any other Grade 3 or Grade 4 toxicity that persists despite optimal medical management	Discontinue acalabrutinib

AE = adverse event; ALT = alanine aminotransferase; ANC = absolute neutrophil count; ALP = alkaline phosphatase; AST = aspartate aminotransferase; G-CSF = granulocyte colony-stimulating factor; PML = progressive multifocal leukoencephalopathy.

Clinical judgment should be used to determine appropriate management of the subject during any AE.

Acalabrutinib may be held for a maximum of 3 consecutive days (6 consecutive doses) from expected dose due to toxicity. Any other clinically important events where dose delays may be considered appropriate by the Investigator, as well as continuation of therapy after a dose is held beyond 3 days, must be discussed with the Medical Monitor. If a dose is missed due to an AE or for any other reason, missed doses should be completed so the subject receives a maximum of 20 doses of study drug, even if this is beyond the 10-day dosing period.

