7. DISCONTINUATION OF TREATMENT AND SUBJECT WITHDRAWAL

7.1 Discontinuation of Study Treatment

Subjects may discontinue study treatment for the following reasons:

- Unable to swallow pills
- Completed treatment
- Pregnancy
- AE
- Investigator's decision
- Subject's withdrawal of consent from study
- Decision by the Sponsor to terminate the study
- Lost to follow-up
- Death
- Other

The Investigator should instruct the subject to contact the site before or at the time if study treatment is stopped. A subject that decides to discontinue study treatment will always be asked about the reason(s) and the presence of any AEs. The date of last intake of study treatment should be documented in the eCRF. Refer to the guidance in Section 6.5.3.

All subjects will be followed through 90 (\pm 7) days after randomization.

Subjects who receive acalabrutinib should have follow up assessments for safety 28 (\pm 3) days after the last dose of acalabrutinib (whether due to discontinuation or completion of dosing). Subjects who have been randomized to the BSC arm should have a follow up assessment for safety 38 (\pm 3) days after randomization.

For the safety and survival follow-up visits, telemedicine is recommended for capturing AEs and concomitant medications. Safety laboratory tests can be done at the hospital or a local laboratory provided the results are ultimately captured in the clinical database for the study.

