9.6 Statistical Analyses

A comprehensive SAP will be developed and finalized before database lock and will describe the subject populations to be included in the analyses, and procedures for accounting for missing, unused, and spurious data. Any deviations from the SAP will be reported in the Clinical Study Report.

The primary analysis of the study will take place when all randomized subjects have been followed for 38 (\pm 3) days from randomization.

An updated analysis for those endpoints requiring 90-day assessments will take place after the last randomized subject has had 90 days follow up from randomization.

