4.4.1 Adverse events

Verbatim descriptions of AEs will be mapped per version 23.0 of the MedDRA thesaurus terms and graded per National Cancer Institute (NCI) CTCAE, v5.0 or higher. Unless stated otherwise, only treatment-emergent adverse events (TEAEs) will be presented in the summaries. For acalabrutinib + BSC subjects, TEAEs are AEs starting or ongoing AEs worsening after the first dose of study treatment and AEs with start date up to the last dose of study treatment plus 28 (±3) days; for BSC only subjects, TEAEs are AEs starting or ongoing AEs worsening after date of randomization and AEs with start date up to 38 (± 3) days after randomization. In the case a subject's actual treatment received is different than their randomized treatment, TEAEs are AEs starting on or after the date of randomization up to the later of 38 (± 3) days after randomization or the last dose of study treatment plus 28 (±3) days. When programmatically assigning the AEs as treatment emergent, the upper window will be used.

The following summaries will be provided:

- A summary of the number and percentage of subjects reporting any TEAE, TEAEs with outcome of death, at least one TEAE of CTCAE grade 3 or higher, at least one serious TEAE, at least one TEAE possibly related to study drug, and at least one TEAE leading to discontinuation of study drug by treatment group.
- A summary of the number of TEAEs, TEAEs with outcome of deaths, TEAEs with CTCAE grade 3 or higher, serious TEAEs, TEAEs possibly related to study drug, and TEAEs leading to discontinuation of study drug by treatment group.
- A summary of the number and percentage of subjects reporting a TEAE by treatment group, SOC and PT.
- A summary of the number and percentage of subjects reporting the most common TEAEs (occurring in at least 5% of overall subjects) by treatment group, SOC and PT.
- A summary of the number and percentage of subjects reporting a TEAE by treatment group, CTCAE grade, SOC and PT. This will include a subset of grade 3 or higher.
- A summary of the number and percentage of subjects reporting a TEAE possibly related to study drug by SOC and PT.
- A summary of the number and percentage of subjects reporting a TEAE leading to discontinuation of study drug by SOC and PT.

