6. DATA MONITORING COMMITTEE

This study will have a DMC. Details of the roles and responsibilities of the DMC and the DMC data review process will be provided in a separate DMC charter. The DMC will be responsible for reviewing the safety data periodically.

The DMC will review the cumulative safety data approximately 28 days after the first 30 subjects (approximately 15 subjects per arm) have been randomized.

In addition, if at any time during the conduct of the study either of the criteria below are met, enrollment of additional subjects will be paused so that the DMC can convene and conduct a full safety review.

- Any death due to acalabrutinib (per Investigator)
- $\geq 20\%$ treatment discontinuation rate due to toxicity attributed to acalabrutinib (per Investigator), when 10 or more acalabrutinib subjects have been treated
- Any Grade 4 hemorrhage due to acalabrutinib (per Investigator)

During the safety review, the DMC will compare the known AE profile associated with acalabrutinib with comprehensive safety data from the current study. The DMC will determine if an unacceptable increase in Grade 3 or higher AEs known to be associated with acalabrutinib has occurred in the study. After their review, the DMC will make a recommendation regarding study continuation, hold, or termination.

At the time of the safety review the DMC will also review all available preliminary efficacy data and will support any health authority interactions or internal discussions based on their review. The study team will remain blinded to the data that the DMC will review until database lock for the primary analysis of the study, which will occur when all randomized subjects have been followed for 38 (± 3) days from randomization.

An updated analysis for those endpoints requiring 90-day assessments will take place after the last randomized subject has had 90 days of follow up from randomization

Details on the outputs that will be provided to the DMC are provided in Section [8.2](#).

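### The primary-analysis lock is counted from randomization but the Arm 1 TEAE window from the last dose, so late subjects with made-up doses can be truncated with no safety update planned

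*SAP*

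**What the plan says.** **Trigger.** Protocol 9.6: "The primary analysis of the study will take place when all randomized subjects have been followed for 38" (±3) days from randomization. SAP Section 6 keeps the study team blinded until the lock for that analysis, "which will occur when all randomized subjects have been followed for 38" (±3) days. Read literally, a lock is allowed once the last subject is between day 35 and day 41.

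**Adverse event windows.** For BSC, Protocol 7.1 says: "Subjects who have been randomized to the BSC arm should have a follow up assessment for safety 38" (±3) days after randomization, and SAP 4.4.1 ends the treatment-emergent adverse event (TEAE) window at the same point. For acalabrutinib, SAP 4.4.1 counts "AEs with start date up to the last dose of study treatment plus 28" (±3) days. The same section settles which edge applies: "When programmatically assigning the AEs as treatment emergent, the upper window will be used". Protocol 8.6.2 ends routine adverse event reporting on the same two clocks.

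**Dosing.** SAP 3.2.2 spreads 20 doses over 10 calendar days (morning start) or 11 (evening start). Protocol 6.1.2 and 6.7 allow a toxicity hold of up to 3 consecutive days (6 doses). Doses missed for any reason are to be completed, up to 20 in all, "even if this is beyond the 10-day dosing period". No limit is given on the total number made up, and Protocol 6.7 leaves continuation after a longer hold to discussion with the Medical Monitor.

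**Later update.** SAP Section 6: "An updated analysis for those endpoints requiring 90-day assessments will take place after the last randomized subject" has reached 90 days; Protocol 9.6 says the same. Neither document describes a safety update, or a cut-off rule for adverse events that start after the primary lock.

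**The concern.** The two clocks agree only while dosing ends by about 10 days after randomization. Each made-up dose can push the Arm 1 window later, but the lock does not move with it. If the lock comes first, the TEAE tables for the last-randomized subjects cover less time than the SAP's own definition, and no planned analysis picks up the remainder.

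Safety is a primary objective, so the observed window should match the defined one. The shortfall past day 41 is also confined to one arm, because only acalabrutinib windows move, and it falls on subjects with interrupted dosing. The safety follow-up visit carries haematology and chemistry as well as adverse events, so laboratory summaries share the problem.

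**Working it through.** All dates are elapsed days after randomization, with the first dose taken on the randomization date.

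**The plan's own figure.** 10 dosing days + 28 = 38, which reproduces the stated trigger. The SAP amendment history says the BSC follow-up was set at 38 days to bring it closer to the timing in the acalabrutinib arm.

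**Formulas.** Let *m* be the number of doses made up.
- Last dose, morning start: ceil((20 + m)/2) − 1
- Last dose, evening start: floor((20 + m)/2)
- Target safety visit: last dose + 28
- End of TEAE window, upper edge: last dose + 28 + 3 = last dose + 31
- BSC: target visit 38, end of window 38 + 3 = 41

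**Numbers put in.**
- m = 0: last dose 10 − 1 = 9 (morning) or 10 (evening)
- m = 2, evening: 22/2 = 11. m = 3, morning: ceil(11.5) − 1 = 11
- m = 6 (one full hold): 13 − 1 = 12 (morning) or 13 (evening)

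| Case | Last dose | Target visit | Window ends | Days still open if lock is on day 35 / 38 / 41 |
|---|---|---|---|---|
| BSC | – | 38 | 41 | 6 / 3 / 0 |
| Arm 1, no doses made up | 9–10 | 37–38 | 40–41 | 5–6 / 2–3 / 0 |
| Arm 1, 2 (evening) or 3 (morning) made up | 11 | 39 | 42 | 7 / 4 / 1 |
| Arm 1, one full 3-day hold | 12–13 | 40–41 | 43–44 | 8–9 / 5–6 / 2–3 |

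The last column applies to the last subject randomized; someone randomized *d* days earlier has *d* fewer days open.

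**Where the target visit itself passes day 41.** This needs a last dose on day 14: m = 8 for an evening start (28/2 = 14) or m = 9 for a morning start (ceil(14.5) − 1 = 14). That is more than one maximum hold.

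**How many subjects.** The SAP gives 62 randomized but the documents give no actual accrual dates. Assume 10 to 14 weeks, i.e. 62/14 = 4.4 to 62/10 = 6.2 per week.
- Lock on day 41: only full-hold Arm 1 subjects randomized in the last 3 days are open. Over 3 days, 4.4 × 3/7 = 1.9 to 6.2 × 3/7 = 2.7 subjects enter both arms together, so about 1 in Arm 1, and only if that subject had a full hold.
- Lock on day 38: without made-up doses, subjects from the last 3 days are open, about 2 to 3 across both arms. With a full hold the span is 6 days, i.e. 3.8 to 5.3 entering, of whom 1.9 to 2.7 are in Arm 1.
- Lock on day 35: without made-up doses the span is 6 days, about 4 to 5 subjects across both arms.

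**The case against.** The strongest reply is that 38 (±3) days is the safety visit and not a free range for the lock. It is the BSC safety follow-up by definition and the nominal Arm 1 visit by arithmetic. Being followed for 38 (±3) days can fairly be read as having completed that visit, when routine adverse event reporting ends. On that reading a BSC subject seen on day 35 has lost nothing, and the upper-edge sentence is only a programming rule for classifying events.

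Much of this stands. A reader might infer that the lock must precede the last subjects' windows in both arms. The documents do not support that: a lock on day 41 closes every BSC window and every Arm 1 window without made-up doses. A reader might also quote a gap of up to 9 days, but that sets the trigger's lower edge (35) against the window's upper edge after a full hold (44). Applying 9 days to accrual in both arms would inflate the count, because it concerns held Arm 1 subjects only.

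Two other tempting inferences go too far. The first is that the toxicity behind a hold would be missed. It arose during dosing and is already recorded; what may be cut is the last few days of a 28 to 31 day period off drug. The second is that every event after the lock goes unanalysed. Deaths enter Day 90 all-cause mortality. Protocol 8.6.2 and 8.6.3 also keep later related serious events reportable and existing events followed, though that is collection and not analysis.

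The reply does not remove the held-subject case. The completed-visit reading is not stated. Even if it were, a visit after one full hold may properly take place up to day 43–44. A visit on its target day (40–41) fits inside the trigger but still leaves 2 to 3 days of the defined window unobserved.

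**Conclusion.** The point holds as a small mismatch between two stated rules. Once two (evening start) or three (morning start) doses are made up, a late-randomized acalabrutinib subject's TEAE window passes the latest trigger date. The excess is 1 day at that point and 2 to 3 days after one full hold. A lock before day 41 would also shorten the upper-edge window of late subjects without made-up doses in either arm; whether that happens depends on the lock date chosen. Non-fatal events in the gap have no planned analysis.

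The consequence is minor: a few days in a few subjects, in safety summaries that SAP 4.4 makes purely descriptive. Day 28 efficacy is complete well before any permitted lock.

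This rests on the first dose falling on the randomization date (a first dose after midnight moves Arm 1 dates one day later), on the trigger being counted in elapsed days, and, for the subject counts only, on the assumed accrual rate.

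**What to change.** In Protocol 9.6 and SAP Section 6, set the primary lock at the point when every randomized subject has completed, or passed the upper limit of, the safety follow-up window: 41 days after randomization for BSC subjects, and last dose + 31 days for acalabrutinib-treated subjects. Alternatively, or in addition, state that the 90-day update re-runs the TEAE and serious adverse event tables. No dosing rule needs to change.

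The cost is about two sentences of wording. The lock may move by a few days (to day 44 rather than 41 if the last subject had one full hold), and a few safety tables are re-run at an update that is already planned.

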7. CHANGES OF ANALYSIS FROM PROTOCOL

N/A

8. APPENDIX

8.1 AESI and ECI definitions

Adverse Event of Special Interest (AESI)

The following preferred terms for the ventricular arrhythmias AESI include:

- Torsade de pointes
- Ventricular arrhythmia
- Ventricular extrasystoles
- Ventricular fibrillation
- Ventricular flutter
- Ventricular tachyarrhythmia
- Ventricular tachycardia

Events of Clinical Interest

The Events of Clinical Interest (ECIs) are from the acalabrutinib program with extended dosing of acalabrutinib in patients with haematologic malignancies.

Category	Subcategory	Definition
Cardiac events		
 • SOC Cardiac disorders
	Atrial fibrillation	
 • PT Atrial fibrillation • PT Atrial flutter
	Ventricular tachyarrhythmias	
 • PT Torsade de pointes • PT Ventricular fibrillation • PT Ventricular flutter • PT Ventricular tachyarrhythmia • PT Ventricular tachycardia
Cytopenias – Anemia		
 • SMQ Haematopoietic erythropenia [narrow + broad]
Cytopenias – Leukopenia		
 • SMQ Haematopoietic leukopenia [narrow + broad]
	Neutropenia	
 • PT Band Neutrophil count decreased • PT Band neutrophil percentage decreased • PT Cyclic neutropenia • PT Febrile Neutropenia • PT Idiopathic neutropenia • PT Neutropenia • PT Neutropenic infection • PT Neutropenic sepsis • PT Neutrophil count decreased • PT Neutrophil percentage decreased
	Other leukopenia	
 • SMQ Haematopoietic leukopenia [narrow + broad] excluding PTs for neutropenia above

Cytopenias - Thrombocytopenia	
 SMQ Haematopoietic thrombocytopenia [narrow + broad]
Hemorrhage	
 SMQ Haemorrhage terms (excl laboratory terms)
Major hemorrhage	
 As per Acerta definition (see below)
Hepatotoxicity	
 SMQ [narrow] Hepatic failure, fibrosis and cirrhosis and other liver damage-related conditions SMQ [narrow] Hepatitis, non-infectious SMQ [narrow] Liver related investigations signs
Hypertension	
 SMQ Hypertension [narrow]
Infections	
 SOC Infections and infestations
Interstitial lung disease/Pneumonitis	
 SMQ [narrow] Interstitial lung disease
Second primary malignancies ^a	
 SMQ Malignant tumours (including Haematological malignant tumours SMQ and Non-haematological malignant tumours SMQ) SMQ Malignant lymphomas [narrow] SMQ Myelodysplastic syndrome [narrow]
Second primary malignancies (excluding non melanoma skin)	
 The above excluding PTs mapping to HLT Skin neoplasms malignant and unspecified (excluding melanoma)
Tumor lysis syndrome ^b	
 PT Tumour lysis syndrome

MedDRA version 23.0

HLT=High-Level Term; PT=Preferred Term; SOC=System Organ Classes; SMQ=Standardized MedDRA Queries.

^a Only flagged as an ECI if malignancy is reported in the subject's medical history and is ongoing.

^b Only flagged as an ECI if tumor lysis syndrome is reported in the subject's medical history and is ongoing.

Major Hemorrhage

Major hemorrhage is defined as any hemorrhagic event that is serious, or Grade ≥ 3 in severity, or that is a CNS hemorrhage (any severity grade).

Search Strategy:

- I. Use standardized MedDRA version 23.0 query:
 - o Haemorrhage terms (excluding laboratory terms) (SMQ) [20000039]
- II. Identify Major Events that are a subset of the Haemorrhage SMQ:
 - o Grade ≥ 3 AE
 - o Any serious adverse event
 - o All grades of CNS hemorrhage

CNS Hemorrhage Preferred Terms (MedDRA Version 23.0)

- Acute haemorrhagic leucoencephalitis
- Basal ganglia haematoma

- Basal ganglia haemorrhage
- Basilar artery perforation
- Brain contusion
- Brain stem haematoma
- Brain stem haemorrhage
- Brain stem microhaemorrhage
- Central nervous system haemorrhage
- Cerebellar haematoma
- Cerebellar haemorrhage
- Cerebellar microhaemorrhage
- Cerebral aneurysm perforation
- Cerebral aneurysm ruptured syphilitic
- Cerebral arteriovenous malformation haemorrhagic
- Cerebral artery perforation
- Cerebral cyst haemorrhage
- Cerebral haematoma
- Cerebral haemorrhage
- Cerebral haemorrhage foetal
- Cerebral microhaemorrhage
- Encephalitis haemorrhagic
- Epidural haemorrhage
- Extradural haematoma
- Haemorrhage intracranial
- Haemorrhagic cerebral infarction
- Haemorrhagic stroke
- Haemorrhagic transformation stroke
- Intracerebral haematoma evacuation
- Intracranial haematoma
- Intracranial tumour haemorrhage
- Intraventricular haemorrhage
- Meningorrhagia
- Ocular retrobulbar haemorrhage
- Optic disc haemorrhage
- Optic nerve sheath haemorrhage
- Pituitary haemorrhage
- Putamen haemorrhage
- Retinal aneurysm rupture
- Retinal haemorrhage
- Retinopathy haemorrhagic
- Ruptured cerebral aneurysm
- Spinal cord haematoma
- Spinal cord haemorrhage
- Spinal epidural haematoma
- Spinal epidural haemorrhage
- Spinal subarachnoid haemorrhage

- Spinal subdural haematoma
- Spinal subdural haemorrhage
- Subarachnoid haematoma
- Subarachnoid haemorrhage
- Subdural haematoma
- Subdural haematoma evacuation
- Subdural haemorrhage
- Subgaleal haematoma
- Subgaleal haemorrhage
- Subretinal haematoma
- Thalamus haemorrhage
- Traumatic intracranial haematoma
- Traumatic intracranial haemorrhage

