2. INTRODUCTION

2.1 Background and Study Rationale

Coronavirus disease 2019 (COVID-19) is a new pandemic disease caused by the severe acute respiratory syndrome coronavirus 2 (SARS-CoV-2). In a retrospective study of 191 patients with COVID-19, sepsis was the most frequently observed complication, followed by respiratory failure, acute respiratory distress syndrome (ARDS), heart failure, and septic shock. While sepsis might be directly caused by SARS-CoV-2 infection, further research is needed to investigate the pathogenesis of COVID-19 illness. Most COVID-19 cases (~80%) are mild respiratory illnesses. 5% to 15% of these respiratory illnesses require hospitalization (mostly due to pneumonia) and can progress quickly to severe acute lung injury and ARDS (Huang et al 2020, Wu and McGoogan 2020, Zhou et al 2020), which is associated with high mortality.

Normally, human coronaviruses are detected and cleared by the immune system, but a subset of patients experience increased severity of symptoms (Channappanavar and Perlman 2017, Zhou et al 2020). These symptoms have been associated with the loss of control of the virally induced immune response (Li et al 2020). In these cases, the inflammatory response is hypothesized to be a major pathogenic mechanism of ARDS through modulation of pulmonary macrophages and dendritic cells (Channappanavar et al 2016, Huang et al 2005, Wong et al 2004, Yoshikawa et al 2009) and/or neutrophils (Herold et al 2015). Putative inflammatory mediators include interleukin (IL)-1 β , IL-6, IL-8, IL-10, tumor necrosis factor alpha (TNF α), and monocyte chemoattractant protein-1 (MCP-1) (Chen et al 2020, Herold et al 2015, Yoshikawa et al 2009). During the acute phase of coronavirus infection, T cells are the critical mediators of clearance of infection, while B cells generate a protective humoral response (Zhao et al 2009, Zhao et al 2014). Generation of antibodies against coronaviruses is not always protective. In a mouse model, an anti-spike immunoglobulins (specific to SARS-COV) could skew the inflammation-resolving response which lead to severe acute lung injury in mice (Liu et al 2019).

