6.6.2 Infections

Serious infections, including fatal events, have been reported in subjects treated with acalabrutinib (eg, aspergillosis). Subjects should be monitored for signs and symptoms of infection and treated as medically appropriate. Please refer to Section 6.7 for study drug modification guidance.

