8.6.10 Disease Progression

Disease progression can be considered as a worsening of a subject's condition attributable to COVID-19 pneumonia for which the investigational product is being studied. It may be an increase in the severity of the disease under study and/or increases in the symptoms of the disease. Events, which are unequivocally due to COVID-19 pneumonia, should not be reported as an AE or SAE during the study. Events attributable to disease progression of COVID-19 include pulmonary failure, ARDS, sepsis, shock, multiorgan failure and death.

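### The infection ECI total can mix COVID-19 events with secondary infections and so mask an excess, and the protocol's reporting rules conflict on serious sepsis

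*SAP*

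**What the plan says.** **Definition.** In SAP 8.1 the infection ECI is "SOC Infections and infestations", the whole system organ class (SOC), with no subcategory. The SAP says that the ECIs "are from the acalabrutinib program with extended dosing of acalabrutinib in patients with haematologic malignancies". Other rows are refined. Leukopenia is split into neutropenia and the rest, second malignancies have a row without non-melanoma skin cancers, and the malignancy row has a condition that starts "Only flagged as an ECI if malignancy is reported in the" and refers to medical history. The infection row has no refinement.

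**Presentation.** SAP 4.4.1.1 summarizes ECIs in the same way as AESIs: by arm, CTCAE grade, group term and preferred term (PT), with relatedness, discontinuation and subject listings. SAP 4.4.1 also tabulates treatment-emergent events by SOC and PT.

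**Reporting of disease events.** Protocol 8.6.10 states: "Events, which are unequivocally due to COVID-19 pneumonia, should not be reported as an AE or SAE during the study". It continues: "Events attributable to disease progression of COVID-19 include pulmonary failure, ARDS, sepsis, shock, multiorgan failure and death". Protocol 8.6.9 says that events unequivocally due to the disease are not reported as AEs, but makes an exception for those that meet SAE criteria or lead to discontinuation. Protocol 8.6 requires a report whenever it is uncertain that the disease alone is the cause.

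**Known risk.** Protocol 6.6.2 states: "Serious infections, including fatal events, have been reported in subjects treated with acalabrutinib". Protocol 2.1, citing one retrospective study of 191 COVID-19 patients, reports that "sepsis was the most frequently observed complication".

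**The concern.** Safety is a primary objective, and infection is a recognised risk of the drug. In Protocol Table 5 it is the largest category at Grade 3 or higher. Protocol 6.5.2 also permits corticosteroids and agents such as tocilizumab alongside acalabrutinib.

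The ECI list was built for a population in which the disease under treatment was not an infection. Here it is. If reported COVID-19 events fall in the same SOC as secondary infections, the group-term row adds together two things on which the drug may act in opposite directions: fewer COVID-19 events if it works, and more secondary infections if it impairs host defence. A randomized control arm does not remove this, because the offset arises from the treatment effect itself.

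Sepsis raises a second question. It is an event in which a drug effect on infection could appear, and the protocol gives two different answers on whether a serious disease-related case is reported. Attribution is made by investigators who know the arm.

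**Working it through.** **1. The plan's own figures.** Table 5 gives infections in 1040 subjects on monotherapy: 694/1040 = 66.7% at any grade and 183/1040 = 17.6% at Grade 3 or higher. Both reproduce, and no stated number is wrong. The point concerns definitions.

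**2. Can COVID-19 events enter the ECI?** Not automatically. A pre-existing condition that has not worsened is not an AE, and neither is progression unequivocally related to COVID-19 pneumonia (Protocol 8.6, SAP 3.2.1). There are three routes in:
- doubtful events (Protocol 8.6);
- serious events or those leading to discontinuation (Protocol 8.6.9);
- disease-related entries collected although they are not AEs by definition, which SAP 4.4.1 expects to list.

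The table specifications in SAP 4.4.1 and 4.4.1.1 contain no rule that removes such entries by term.

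**3. What do the planned outputs give?** The group-term row counts subjects with any term in the SOC. PT rows show COVID-19 terms on separate lines, but PT rows cannot be summed to subjects, because a subject with two PTs appears in both rows. The number of subjects with any non-COVID infection is therefore not tabulated. It could be rebuilt from listings, but the terms to exclude would then be chosen after the data were seen by arm.

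**4. Illustration (all infection rates assumed).** Let s be the rate of secondary infection and c the rate of COVID-coded events. If they are independent, the SOC rate is 1 − (1 − s)(1 − c). Take s = 10% on BSC and 25% on acalabrutinib, a true excess of 15 points.

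| c, BSC | c, acalabrutinib | SOC, BSC | SOC, acalabrutinib | Apparent difference |
|---|---|---|---|---|
| 0% | 0% | 10.0% | 25.0% | +15.0 |
| 10% | 10% | 19.0% | 32.5% | +13.5 |
| 30% | 30% | 37.0% | 47.5% | +10.5 |
| 30% | 20% | 37.0% | 40.0% | +3.0 |
| 30% | 10% | 37.0% | 32.5% | −4.5 |

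In the last row, BSC is 1 − 0.90 × 0.70 = 0.370 and acalabrutinib is 1 − 0.75 × 0.90 = 0.325. The values of c are the planned success rates of 70% and 90% (Protocol 9.2) read as failures, which is itself an assumption.

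Other values of s, comparing c = 0 in both arms with c = 30% vs 10%:
- 5% vs 15%: from +10 to −10 points (33.5% vs 23.5%).
- 10% vs 30%: from +20 to 0 points (37.0% in both arms).

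The last row of the table does not depend on independence if both arms have the same overlap pattern. With the two event types in separate subjects it is 40% vs 35%; with full overlap it is 30% vs 25%. Both give −5 points. The 30%/30% row is more sensitive: +15 with separate subjects (40% vs 55%) and 0 with full overlap (30% vs 30%).

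**5. Sepsis.** Take a life-threatening sepsis that the investigator judges unequivocally due to COVID-19 pneumonia. It meets the SAE criteria in Protocol Appendix B 2. Under 8.6.9 it is reported; under 8.6.10 it is not. Both rules cannot be followed. With 62 randomized (SAP 1.3), assumed to be 31 per arm, one unrecorded case lowers that arm's ECI rate by 1/31 = 3.2 points, but only if the subject has no other recorded infection term.

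**The case against.** **Separation is largely available.** PT-level tables by arm and grade, and listings of all AEs, SAEs and ECIs, let a reader of a 62-subject trial set COVID-19 terms aside. This stands in good part. A reader might infer that the infection risk cannot be separated from COVID-19 at all, and the documents do not support that. What is missing is a pre-specified subject-level count.

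**The ECI does not count every subject's qualifying infection.** A reader might infer this from the whole-SOC definition. It is wrong, for the reasons in step 2 of the working. Respiratory worsening and ARDS may also code elsewhere; the documents do not list the PTs in the SOC.

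**The sepsis list is conditional.** A reader might infer that sites are told in advance to attribute all sepsis to COVID-19. The preceding sentence limits the rule to unequivocal events, doubtful cases must be reported, and Protocol 6.7 treats confirmed bacterial and severe opportunistic infections as events in their own right. Protocol 2.1 also allows that the virus may cause sepsis directly, which is a reason for the listing. All of this stands. It leaves the conflict between 8.6.9 and 8.6.10 untouched.

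**The rates are invented, and the trial is small.** True. Even a clean comparison of 25% vs 10% with 31 per arm has a 90% half-width of 1.645 × √((0.25 × 0.75 + 0.10 × 0.90)/31) = 15.6 points. The gain is an interpretable summary, not the power to establish an excess.

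**Conclusion.** The pre-specified infection summary can mix reported COVID-19 events with secondary infections, and its subject-level total can understate, cancel or reverse an excess of secondary infections if acalabrutinib reduces COVID-19 progression. In the assumed scenarios a true +15 points appears as anything from +13.5 to −4.5 points. These figures show direction and possible size; they are not estimates.

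Separately, Protocol 8.6.9 and 8.6.10 contradict each other on serious disease-related events, so sepsis and shock may be recorded inconsistently. The two problems can act in opposite directions on the total: COVID-19 terms inflate it and unrecorded sepsis deflates it. The documents do not show that either has occurred.

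The conclusion assumes that COVID-19 and sepsis terms code to this SOC, that some disease events are reported by the routes described, and that the arms are of about equal size. The change is worth making because it is cheap and bears on a primary-objective safety summary.

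**What to change.** 1. **SAP 8.1, before database lock.** Add two subcategories under infections, on the pattern already used for leukopenia: *SARS-CoV-2/COVID-19 terms* and *Infections excluding SARS-CoV-2/COVID-19 terms*. Fix the PT list in advance. Use the second, as subjects by arm and CTCAE grade, as the infection-risk summary, shown beside the SOC total. Cost: one PT list and one or two table rows.

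2. **Protocol 8.6.9 and 8.6.10.** Reconcile them so that one rule governs serious disease-related events, and check that 8.6.11 on deaths agrees with it. Removing sepsis and shock from the list would not be enough, since the exclusion of unequivocal disease events would remain. Recruitment was complete at 62 when SAP version 3.0 was written, so a new collection rule could also apply unevenly to earlier and later events.

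3. **Sepsis and shock.** Tabulate by arm all such events recorded anywhere in the database, whatever their attribution, and state in the study report which reporting rule sites followed. Cost: one further table. It cannot recover events that were never recorded.
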